7.4 Secondary Safety Endpoints

The following safety parameters for the study drug (CT-P10, Rituxan and MabThera) will be determined as secondary safety endpoints:

- Immunogenicity testing
- Immunoglobulin (IgM, IgG and IgA) testing
- Hypersensitivity monitoring via vital sign measurements (including blood pressure, heart and respiratory rates, and temperature) and ECGs
- Vital sign measurements
- ECGs
- Signs and symptoms of TB monitoring
- Physical examination findings
- AEs
- Infections
- Infusion related reactions (IRRs)
- Clinical laboratory analyses
- Pregnancy testing
- Concomitant medications

7.5 Sample Size Calculations

Part 1 of this study is powered to demonstrate PK similarity of CT-P10, Rituxan and MabThera in AUC_{0-last}, AUC_{0- ∞} and C_{max}. Similarity will be demonstrated if the 90%

confidence interval (CI) for the geometric mean ratio of CT-P10 to Rituxan and MabThera in AUC_{0-last} , $AUC_{0-\infty}$ and C_{max} is within the bounds of 80% and 125%.

In Part 1, based on overall 90% power, 2-sided alpha equal to 0.1, an interpatient coefficient of variation (CV) in AUC_{0-last} of 30%, and a true of geometric mean equal to 1, fifty patients are needed in each treatment group being compared (50 patients in the CT-P10 treatment group, 50 patients in the MabThera treatment group, and 50 patients in the Rituxan treatment group: 150 patients total). The statistical power of each comparison, CT-P10 versus MabThera, CT-P10 versus Rituxan and MabThera versus Rituxan is 96.5% to achieve overall 90% power accounting for multiplicity with type II error correction. Allowing for a drop-out rate of 20%, 189 patients will be randomly assigned into the study in a 1:1:1 allocation.

In Part 2, the sample size of 322 evaluable patients (133 patients in the CT-P10 group and 189 patients in the reference products group [Rituxan and MabThera groups]) leads to approximately 90% power for the demonstration of similarity based on a two-sided 90% CI for the difference of mean change of DAS28 score at Week 24 from baseline value between CT-P10 and reference products for an equivalence margin of ± 0.50 . In the sample size calculation, the common standard deviation of the mean change of DAS28 at Week 24 from baseline is assumed as 1.32 based on the CT-P10 1.1 study result for the therapeutic equivalence margin of ± 0.50 . Incorporating hypothesized drop-out rate of 10%, total sample size of 361 subjects (149 eligible patients in the CT-P10 and 212 eligible patients in the reference products group [Rituxan and MabThera groups], including up to 63 patients from each of the CT-P10, Rituxan and MabThera groups in Part 1) will be used in evaluation of efficacy endpoints.

In total, approximately 361 patients will be available for analysis (a total of approximately 149 patients for the CT-P10 group and 212 patients for the reference products group, including up to 63 patients from each treatment group in Part 1).

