CT-P10 is being developed by CELLTRION, Inc. as a biosimilar candidate of Rituxan and MabThera, a compound with established efficacy in the treatment of active RA (MabThera 2015; Rituxan. 2014). Rituximab is approved as Rituxan in the United States and as MabThera in other countries. CT-P10 can offer a more affordable treatment for RA than the originator protein if similar efficacy and safety are demonstrated and allow increased access to this valuable drug with a proven mechanism of action in RA patients.

The pharmacokinetic (PK) profile is expected to be similar to that of Rituxan and MabThera. There will be 2 serum peaks of CT-P10 at the end of the IV infusions that will be

administered on Day 0 and Day 14: the peak concentrations will be approximately 400 μ g/mL with a standard deviation (SD) of $\pm 200 \mu$ g/mL. Serum levels will decrease slowly after maximum serum concentration (C_{max}) has been reached. The terminal elimination half-life (t_{1/2}) of CT-P10 is expected to be approximately 20 days (SD of \pm several days).

This is a similarity study that consists of 3 parallel arms of Rituxan (US-licensed), MabThera (EU-approved), and CT-P10. All statistical assessments will be direct comparisons between the treatment groups at corresponding time points.

The PK sampling time design is based on mean MabThera $t_{1/2}$ of approximately 20.8 days in patients with RA (MabThera 2015) and on published PK studies (Breedveld et al 2007; Tran et al 2010). The area under the concentration-time curve from time zero to time of last quantifiable concentration (AUC_{0-last}), the area under the concentration-time curve from time zero to infinity (AUC_{0- ∞}) and C_{max} (after the second infusion) from the first course of treatment were selected as the co-primary PK endpoints.

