### 5.2. Sample Size

For Part 1, 189 patients will be randomized in a 1:1:1 ratio to the CT-P10, Rituxan, and MabThera groups. Later, for Part 2, 172 patients will be allocated in a 1:1 ratio to the CT-P10 and Rituxan groups.

Part 1 of this study is powered to demonstrate PK similarity of CT-P10, Rituxan, and MabThera in  $AUC_{0-last}$ ,  $AUC_{0-\infty}$ , and  $C_{max}$ . Similarity will be demonstrated if the 90% confidence interval (CI) for the geometric mean ratio of CT-P10 to Rituxan and MabThera in  $AUC_{0-last}$ ,  $AUC_{0-\infty}$ , and  $C_{max}$  is within the bounds of 80% and 125%.

In Part 1, based on overall 90% power, Two one-sided alpha equal to 0.05, an interpatient CV in  $AUC_{0-last}$  of 30%, and a true of geometric mean equal to 1, fifty patients are needed in each treatment group being compared (50 patients in the CT-P10 treatment group, 50 patients in the MabThera treatment group, and 50 patients in the Rituxan treatment group: 150 patients total). The statistical power of each comparison, CT-P10 versus MabThera, CT-P10 versus Rituxan,

and MabThera versus Rituxan is 96.5% to achieve overall 90% power accounting for multiplicity with type II error correction. Allowing for a drop-out rate of 20%, 189 patients will be randomly assigned into the study in a 1:1:1 allocation.

In Part 2, the sample size of 322 evaluable patients (133 patients in the CT-P10 group and 189 patients in the reference products group [Rituxan and MabThera groups]) leads to approximately 90% power for the demonstration of similarity based on a two-sided 90% CI for the difference of mean change of DAS28 (CRP) score at Week 24 from baseline value between CT-P10 and reference products for an equivalence margin of  $\pm 0.50$ . In this sample size calculation, the common standard deviation of the mean change of DAS28 at Week 24 from baseline is assumed as 1.32 based on the CT-P10 1.1 study result for the therapeutic equivalence margin of  $\pm 0.50$ . Incorporating hypothesized drop-out rate of 10%, total sample size of 361 subjects (149 eligible patients in the CT-P10 and 212 eligible patients in the reference products group, including up to 63 patients from each of the CT-P10, Rituxan, and MabThera groups in Part 1) will be used in evaluation of efficacy endpoints.

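### Part 1 claims 90% overall power for AUC0-last, AUC0-∞ and Cmax but is sized on AUC0-last alone; with the Cmax spread in the protocol's Introduction, power is about 25%

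*Protocol*

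**What the plan says.** Protocol 7.5 opens with the claim "Part 1 of this study is powered to demonstrate PK similarity of CT-P10, Rituxan and MabThera in" AUC0-last, AUC0-∞ and Cmax. SAP 5.2 makes the same claim.

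The inputs that follow are: "based on overall 90% power, 2-sided alpha equal to 0.1, an interpatient coefficient of variation (CV) in AUC_{0-last} of 30" per cent, "and a true of geometric mean equal to 1", and 50 evaluable patients per arm. The SAP writes the error rate as "Two one-sided alpha equal to 0.05", which is the same test as a 90% confidence interval. The power of each of the three treatment comparisons "is 96.5% to achieve overall 90% power accounting for multiplicity with type II error correction". A 20% drop-out allowance takes the total to 189 randomised, 63 per arm. The synopsis uses the same single CV.

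On the success rule, Protocol 7.8.1.1 concludes similarity only if the 90% intervals for every pair of the three products lie within 80–125% for all three parameters. That is nine intervals.

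On Cmax variability, the only figures in either document are in Protocol Section 1 (Introduction). There "the peak concentrations will be approximately 400" µg/mL "with a standard deviation (SD) of $\pm 200 \mu$ g/mL", stated for the peaks after both the Day 0 and the Day 14 infusions.

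**The concern.** The claim covers three parameters and the calculation covers one. All co-primary parameters must pass, so each added parameter lowers the chance of success. That loss appears nowhere in the sizing. The parameter left out that matters most is Cmax, because the Introduction's figures make it clearly more variable than the 30% used for AUC0-last.

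This is the primary objective of Part 1. A reader is told that identical products would fail only about one time in ten. If Cmax is as variable as the Introduction suggests, failure is the likelier result even when the products are identical, and a Cmax miss could then be read as a product difference.

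**Working it through.** **Inputs.** Margin 80–125%, true ratio 1, 5% per side, 50 evaluable per arm, AUC0-last CV 30% (Protocol 7.5, SAP 5.2). Cmax CV = 200/400 = 50% (Protocol Section 1). Correlations between parameters are not in the documents, so a range is assumed.

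**Method.** Two one-sided tests on the log scale for parallel groups: σ = √ln(1 + CV²), SE = σ√(2/n), limits ±ln 1.25 = ±0.2231. The normal approximation is 2Φ(0.2231/SE − 1.645) − 1. Exact values integrate over the distribution of the estimated variance. Joint power over three arms and three parameters was simulated with a pooled variance.

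**1. The plan's own figure (CV 30%, n = 50).**
- σ = 0.2936 and SE = 0.2936 × √(2/50) = 0.0587.
- 2Φ(3.80 − 1.645) − 1 = 96.9%; exact 96.7%. Stated: 96.5%.
- Overall: 1 − 3 × 0.035 = 89.5%, or 0.965³ = 89.9%. Stated: 90%. Simulated joint power for the three pairs is 91.8%.
- Drop-out: 50/0.8 = 62.5, so 63 per arm and 189 in total.

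The figure is sound for one parameter. The 3 × 0.035 uses up the whole type II allowance on three comparisons.

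**2. Cmax at CV 50% (n = 50).**
- σ = 0.4724 and SE = 0.4724 × √(2/50) = 0.0945.
- 2Φ(2.36 − 1.645) − 1 = 52.7%; exact 51.7% per comparison.
- All three pairs on Cmax: 24.4%.
- 96.5% per comparison would need about 127 evaluable per arm (127/0.8 = 158.75, so 159 randomised), against 50 (63) planned.

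**3. All nine intervals (n = 50), by assumed common correlation between parameters.**

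| CVs: AUC0-last / AUC0-∞ / Cmax | 0.5 | 0.8 | 0.95 |
|---|---|---|---|
| 30 / 30 / 30% | 80% | 84% | 88% |
| 30 / 30 / 40% | 51% | 56% | 57% |
| 30 / 30 / 50% | 22% | 25% | 25% |

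With the two AUCs correlated 0.95 and the AUC–Cmax correlation between 0 and 0.7, the results are 82–85% (all CVs 30%) and 22–24% (Cmax CV 50%).

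**4. Sensitivity of Cmax alone, three pairs, n = 50.** CV 35%: 76%. 40%: 57%. 45%: 39%. 50%: 24%. Power falls below one half at a CV of about 42%.

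**The case against.** The strongest objection is that 400 ± 200 is not a sizing input. It is a rounded description of the expected profile, given for both peaks together, whereas the co-primary Cmax is the second-infusion peak only. Treating 50% as that peak's between-patient CV is an inference, and step 4 shows how much the answer depends on it. This stands, and the 25% has to be read as conditional. It remains the only Cmax variability in either document, and any value from 35% upwards still leaves Cmax alone well below 90% at 50 per arm.

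Three further choices lean towards low power:

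- **Success rule.** Protocol 7.5 and SAP 10.3 word the criterion as CT-P10 against each reference. On that reading Cmax power at CV 50% is 30%. Protocol 2.1.1 and 7.8.1.1 include Rituxan against MabThera.
- **Covariates.** The primary model is an ANCOVA, and SAP 10.3 removes outliers from the primary analysis. If covariates explained 10, 20 or 30% of the log variance (assumed), three-pair Cmax power would be 32, 42 or 53%.
- **Completers.** If all 63 per arm were evaluable, it would be 42%.

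None of these restores 90% at a 50% CV.

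If every CV were 30%, some favourable cases do reach 90%. With no drop-out the nine intervals pass with 93–96%, and on the narrower rule at correlation 0.95 power is about 91%. The plan states its power at 50 per arm with 20% drop-out, and relies on neither case.

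It is also fair that low power is the sponsor's risk. It does not inflate false claims of similarity or alter the decision rule. It does make the stated power wrong.

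**Conclusion.** The concern holds. The mismatch between the claim and its basis needs no assumption about Cmax: 90% overall power is a one-parameter result attached to a three-parameter criterion. With every CV at 30% and 50 per arm, the nine-interval criterion is met with probability 80–88% over the correlations considered.

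The size of the shortfall does depend on Cmax. On the Introduction's figures it is 52% per comparison, 24% for three pairs and 22–25% for all nine intervals. Those values assume that 400 ± 200 describes between-patient spread of the second-infusion peak, log-normal Cmax, AUC CVs of 30%, no variance removed by covariates, 50 evaluable per arm, and all three pairs required. Relaxing the last three assumptions one at a time gives 30–53% for Cmax alone, still far short of 90%.

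**What to change.** In Protocol 7.5, the synopsis and SAP 5.2:

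- State that 90% overall power applies to AUC0-last across the three comparisons only.
- Give planning CVs for AUC0-∞ and Cmax, with their source.
- Report the power for Cmax and for all nine intervals at those CVs, with the assumed correlations. With the figures now in the documents this is about 22–25% at a Cmax CV of 50%, and 80–88% if every CV is 30%.
- Use one success rule throughout (all pairs, or CT-P10 against each reference), so that the power refers to a defined criterion.

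If 400 ± 200 is not the planning value for the second-infusion Cmax, correct or qualify it in Protocol Section 1 and put the planning value in its place.

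The cost is wording only, with no added patients. The stated power becomes less favourable.

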7.6 Analysis Sets

Five patient populations are defined: PK, efficacy, PD, safety, and all-randomized populations.

The PK population is defined to be all patients who receive at least 2 doses (Week 0 and Week 2) of study drug (CT-P10, Rituxan or MabThera), who provide sufficient blood concentration data to compute the required PK variables, and who do not have any major protocol violation including a violation of the inclusion and exclusion of criteria. The PK population will be the primary population for the summary and analysis of PK data.

The efficacy population is defined to be all patients who receive at least 1 dose of study drug (CT-P10, Rituxan or MabThera), who have at least 1 post-treatment efficacy result, and who do not have any major protocol violation including a violation of the inclusion and exclusion of criteria. The efficacy population will be the primary population for the summary of efficacy data.

The PD population is defined to be all patients receiving at least 1 dose of study drug (CT-P10, Rituxan or MabThera) and providing at least 1 post-treatment PD result. The PD population will be the primary population for the summary of PD data.

The safety population is defined to be all patients who receive at least 1 dose (full or partial) of study drug (CT-P10, Rituxan or MabThera). The safety population will be the primary population for the summary of safety data.

The all-randomized population is defined to be all patients enrolled and randomly assigned to receive a dose of study drug, regardless of whether or not any study drug dosing was completed. All efficacy parameters will also be analyzed for the all-randomized population.

The number of patients, who discontinue from the study prematurely, together with the reasons for discontinuation, will be summarized. In addition, for each analysis population the number of patients will be presented.

7.7 Description of Subgroups to be Analyzed

Subgroup analysis could be implemented to reflect medical, regulatory, regional, or ethnic considerations.

7.8 Statistical Analysis

Statistical analyses will be carried out using

. The statistical methods for this study, summarized below, will be described in a detailed statistical analysis plan (SAP), which will be finalized prior to locking of the database and unblinding of the treatment codes. Changes from analyses planned in this protocol will be documented in the SAP. Any deviations from the planned analysis as described in the SAP will be justified and recorded in the final study report.

Continuous variables will be summarized by reporting the number of observations, mean, SD, median, minimum, and maximum. Categorical variables will be summarized using frequency tables showing the number and percentage of patients within a particular category.

Pharmacokinetic parameters will be computed by noncompartmental methods using appropriate validated software such as WinNonlin (Pharsight, St Louis, Missouri).

The following pair-wise treatment comparisons will be made for the Part 1 analyses:

- CT-P10 vs. Rituxan
- CT-P10 vs. MabThera
- Rituxan vs. MabThera

For the Part 2 analyses up to Week 48, patients from Rituxan and MabThera treatment groups will be combined as a reference products groups.

7.8.1 Pharmacokinetic Analyses

All PK analyses will be performed based on the results from Week 0 to Week 48.

7.8.1.1 Co-primary Pharmacokinetic Analysis

The primary PK analysis will assess the similarity of CT-P10, Rituxan and MabThera in terms of AUC_{0-last} (over both infusions of the first course of treatment, from time zero to the last measurable concentration), $AUC_{0-\infty}$ (over both infusions of the first course of treatment, from time zero to infinity) and C_{max} (after the second infusion of the first course of treatment) as co-primary PK endpoints.

The following PK parameters as co-primary PK endpoints will be calculated using noncompartmental methods:

- AUC_{0-last} will be calculated using trapezoidal rule. This will be calculated over both infusions in the first course of treatment.
- AUC_{0-∞} will be calculated using trapezoidal rule. This will be calculated over both infusions in the first course of treatment.
- C_{max} will be calculated after the second infusion in the first course of treatment.

In each part, for the calculation of PK parameters, all serum concentrations that are below the quantification limit (BQL) prior to the first measurable concentration will be set to zero. The BQL values after the first dose will be set equal to the lower limit of quantification. Actual sampling times, rather than scheduled sampling times, will be used in all computations of PK parameters.

- The primary PK parameter estimates will be analysed using an analysis of covariance (ANCOVA) with treatment as a fixed effect and country, gender, race, prior anti-TNFalpha (anti-TNF α) blocker status (inadequate response versus intolerant case), and RF or anti-CCP status (both positive versus both negative versus either RF or anti-CCP negative) fitted as covariates. If country is found to be unsuitable as a covariate due to the number of levels, then this may be pooled into a new variable, region defined in the SAP, for use as a covariate. Point estimates (geometric means and ratio of geometric means) will be calculated from back transforming the least squares means of the natural log-transformed values of AUC_{0-last}, AUC_{0- ∞} and C_{max}, and 90% CIs for the ratio of the geometric means of the 2 treatments (CT-P10 versus Rituxan, CT-P10 versus MabThera, and Rituxan versus MabThera) will also be produced. AUC_{0-last}, AUC_{0- ∞}, and C_{max} will be summarized by treatment. Summary statistics will include the mean, SD, median, minimum, maximum, geometric mean, and CV.
- The similarity of pharmacokinetics between CT-P10, Rituxan and MabThera will be concluded if the 90% CIs for the ratios of geometric means based on all the combinations of the three treatments in a pairwise comparison are entirely contained within 80% to 125% for AUC_{0-last}, AUC_{0-∞}, and C_{max}. The equivalence margin of 80% 125% is the universal standard PK similarity margin.

Serum concentrations of study drugs will be summarized by treatment at each scheduled collection time. In addition to the standard summary statistics, the geometric mean and CV will also be presented at each time point. Mean serum concentration time profiles of study drugs will be plotted by treatment on linear and semilogarithmic scales based on scheduled sample times. Individual concentrations and scheduled and actual sample times will be presented in data listings by treatment.

7.8.1.2 Secondary Pharmacokinetic Analysis

For patients in Part 1, the following secondary PK parameters will be considered: $AUC_{0-day14}$ (over both infusions of the first course of treatment, from time zero to Day 14), V_d, CL, t_{1/2} (after the second infusion in the first course of treatment), T_{max} (after both the first and second infusions in the first course of treatment), C_{max, 1} (after the first infusion in the first course of treatment), C_{min} (at Week 24), C_{trough} (prior to the second infusion in the first course of treatment).

For patients in Part 2, the following secondary PK parameters will be considered: T_{max} (after both the first and second infusions in the first and second courses of treatment), C_{max} (after

Protocol Version 5.1, including Country-Specific Protocol Amendment 1 (US) – 01 April 2016 Page 78

both the first and second infusions in the first and second courses of treatment), C_{min} (at Week 24), and C_{trough} (prior to the second infusion in the first and second courses of treatment).

These PK variables will be presented in listings and summarized in tables. For PK parameters, the summary tables will display the following descriptive statistics: n, mean, median, SD, minimum, maximum, geometric mean, and CV.

7.8.2 Efficacy Analyses

7.8.2.1 Primary Efficacy Analysis

The primary efficacy analysis includes patients from Part 1 and Part 2. The primary analysis for DAS28 is an analysis of covariance (ANCOVA) comparing the change from baseline of DAS28 after 24 weeks of treatment between two treatment groups, CT-P10 and reference products, considering the treatment as a fixed effect and country, gender, race, prior anti-TNF- α blocker status (inadequate response versus intolerant case), and RF or anti-CCP status (both positive versus both negative versus either RF or anti-CCP negative) fitted as covariates. If country is found to be unsuitable as a covariate due to the number of levels, then this may be pooled into a new variable, region defined in the SAP, for use as a covariate.

Similarity for the change from baseline of DAS28 (CRP) at week 24 will be evaluated based on the two-sided 90% confidence interval obtained from the ANCOVA model for the difference of means of the change in DAS28 (CRP) between the two treatment groups. The equivalence margin for the 90% CI is defined as [-0.50, 0.50].

7.8.2.2 Secondary Efficacy Analyses

ACR20, ACR50, and ACR70

A patient is defined as a responder according to ACR20 criteria if the following are fulfilled:

- A decrease of at least 20% in the number of tender joints
- A decrease of at least 20% in the number of swollen joints, and
- A 20% improvement in 3 of the following:
 - Patient's assessment of pain on the VAS
 - Patient's global assessment of disease activity (VAS)
 - Physician's global assessment of disease activity (VAS)
 - HAQ estimate of physical ability
 - Serum CRP concentration or ESR

The VAS range is 0 to 10 cm, with higher scores indicating poorer status or more severe pain.

The following categories of patients are considered nonresponders at each week respectively:

- Patients with an improvement according to the ACR criteria of less than 20%
- Patients who discontinue the study prior to the week of interest, except for safety reasons
- Patients with missing data for the evaluation of ACR20 at the week of interest
- Patients with protocol prohibited changes in medication including initiation therapy with a new disease-modifying antirheumatic drugs, increase in dose of RA medication (MTX or corticosteroid), and administration of intra-articular corticosteroids
- Patients requiring a surgical joint procedure during the study

The ACR50 and ACR70 are calculated similarly to ACR20, however, an increase or decrease of 50% and 70%, respectively, must be achieved.

The proportion of patients demonstrating ACR20, ACR50, and ACR70 (based on 1995 ACR criteria) will be summarized by treatment at Week 24, Week 48, and Extension Week 24.

The mean change in the components of the ACR criteria from Baseline will be summarized for ACR20, ACR50, ACR70, and hybrid ACR.

Time to onset of the ACR20 response will also be summarized by treatment.

Hybrid ACR

The hybrid ACR is an outcome measure that combines the ACR20, the ACR50, and the ACR70 and a continuous score of the mean improvement in core set measures (American College of Rheumatology Committee to Reevaluate Improvement Criteria 2007). The score is determined by calculating the mean percentage change in core set measures and reading the score from Table 2 using the patient's ACR status.

	Mean % Change in Core Set Measures									
ACR Status	<20	≥20, <50	≥50, <70	≥70						
Not ACR20	mean % change	19.99	19.99	19.99						
ACR20 but not ACR50	20	mean % change	49.99	49.99						
ACR50 but not ACR70	50	50	mean % change	69.99						
ACR70	70	70	70	mean % change						

Table 2Scoring Method for Hybrid ACR

Abbreviations: ACR, American College of Rheumatology; ACR20, ACR 20% improvement criteria; ACR50, ACR 50% improvement criteria; ACR70, ACR 70% improvement criteria. Source: American College of Rheumatology Committee to Reevaluate Improvement Criteria 2007.

Disease Activity Score Using 28 Joint Count Data

The DAS28 data will be listed and summarized by treatment (including ESR and CRP levels). In addition, change from Baseline will also be summarized, by treatment, for assessments after the first infusion.

European League Against Rheumatism Response Criteria

The DAS-based EULAR response criteria will be summarized by treatment.

Simplified Disease Activity Index and Clinical Disease Activity Index

Simplified and clinical disease activity will be measured using the SDAI and CDAI (Aletaha and Smolen 2009) calculated from the formulas presented in Table 3.

SJC28 + TJC28 + PGA + EGA

Form	nulas	
	Index	Formula
	SDAI	SJC28 + TJC28 + PGA + EGA + CRP

Table 3 Simplified Disease Activity Index and Clinical Disease Activity Index

Abbreviations: CDAI, clinical disease activity index; CRP, C-reactive protein; EGA, evaluator's global assessment of disease activity (physician's global assessment); PGA, patient's global assessment of disease activity; SDAI, simplified disease activity index; SJC, swollen joint count; TJC, tender joint count. Source: Aletaha and Smolen 2009.

Joint Damage Progression

CDAI

Joint damage progression based on radiographic evaluations (1 image of both the right and left hands and both the right and left feet for a total of 4 images) will be assessed by the change in the van der Heijde modification of the Sharp scoring system at Week 48, Extension Week 24 and the EOS visit (van der Heijde 1992). Hand and foot x-rays will be evaluated centrally by independent reviewers for reporting purposes and on a local level for treatment practice.

Health Assessment Questionnaire Disability Index and Short Form-36

The HAQ disability index and SF-36 data will be listed and summarized by treatment. Summaries will be included for the SF-36 physical component score and the mental component score.

